9.5 Subsequent Therapy After Discontinuation of Study Treatment

Once a subject has permanently discontinued study treatment, every effort should be made to have the subject complete the Post-Treatment/Early Termination follow-up visit prior to initiating any subsequent anticancer therapy (approved or investigational). Post-study anticancer therapy will not be provided as part of this study. The subject may receive subsequent anticancer therapy at the discretion of the treating physician. The subsequent anticancer therapy should be documented on the eCRF.

9.6 Evaluation of Response to Subsequent Anticancer Therapy

To identify a potential epigenetic priming effect of tazemetostat, subjects who are withdrawn from this study due to disease progression and who go on to receive subsequent induction therapy should be followed for response whenever possible. Data to be recorded on the subsequent regimen should include:

- Agents received
- Best response
- Duration of response

10 ADVERSE EVENTS AND SERIOUS ADVERSE EVENTS

10.1 Definitions

10.1.1 Adverse Event (AE)

An AE is any untoward medical occurrence in a patient or clinical investigation subject administered a medicinal product and which does not necessarily have to have a causal relationship with this treatment. An AE can therefore be any unfavorable and unintended sign (including an abnormal laboratory finding), symptom, or disease temporally associated with the use of an investigational product, whether or not related to the investigational product.

Worsening of a pre-treatment event, after initiation of tazemetostat, must be recorded as a new AE. For example, if a subject experiences mild intermittent dyspepsia prior to dosing tazemetostat, but the dyspepsia becomes severe and more frequent after the first dose of tazemetostat, a new AE of severe worsening dyspepsia (with the appropriate date of onset) should be recorded in the eCRF.

“Lack of efficacy” or “failure of an expected pharmacological action” *per se* is not to be reported as an AE or SAE. However, any signs and symptoms and/or clinical sequelae resulting from “lack of efficacy” will be reported as an AE or SAE, if they fulfill the definition of an AE or SAE.

Events that **do not** meet the definition of an AE include:

- Medical or surgical procedure (e.g., endoscopy, appendectomy); the condition that leads to the procedure is an AE.
- Situations where an untoward medical occurrence did not occur (social and/or convenience admission to a hospital).
- Anticipated day-to-day fluctuations of pre-existing disease(s) or condition(s) present or detected at the start of the study that do not worsen.

10.1.2 Serious Adverse Event (SAE)

An SAE is any untoward medical occurrence that, at any dose:

- Results in death
- Is life threatening
- **NOTE:** The term 'life threatening' in the definition of 'serious' refers to an event in which the subject was at risk of death at the time of the event. It does not refer to an event, which hypothetically might have caused death, if it were more severe.
- Requires hospitalization or prolongation of existing hospitalization
NOTE: In general, hospitalization signifies that the subject has been detained (usually involving at least an overnight stay) at the hospital or emergency ward for observation and/or treatment that would not have been appropriate in the physician’s office or

out-patient setting. Complications that occur during hospitalization are AEs. If a complication prolongs hospitalization or fulfills any other serious criteria, the event is serious. When in doubt as to whether “hospitalization” occurred or was necessary, the AE should be considered serious.

Hospitalization for elective treatment of a pre-existing condition that did not worsen from baseline is not considered an AE.

- Results in disability/incapacity, or

NOTE: The term disability means a substantial disruption of a person’s ability to conduct normal life functions. This definition is not intended to include experiences of relatively minor medical significance such as uncomplicated headache, nausea, vomiting, diarrhea, influenza, and accidental trauma (e.g., sprained ankle) which may interfere or prevent everyday life functions but do not constitute a substantial disruption.

- Is a congenital anomaly/birth defect.
- Medical or scientific judgment should be exercised in deciding whether reporting is appropriate in other situations, such as important medical events that may not be immediately life threatening or result in death or hospitalization but may jeopardize the subject or may require medical or surgical intervention to prevent one of the other outcomes listed in the above definition. These should also be considered serious. Examples of such events are intensive treatment in an emergency room or at home for allergic bronchospasm, blood dyscrasias or convulsions (in subjects without pre-existing seizure disorder) that do not result in hospitalization, or development of drug dependency or drug abuse.

10.1.3 Adverse Drug Reaction (ADR)

Adverse drug reaction (ADR) is defined as all noxious and unintended responses to a medicinal product related to any dose. An adverse reaction, in contrast to an AE, is characterized by the fact that a causal relationship between a medicinal product and an occurrence is suspected.

10.1.4 Suspected Unexpected Serious Adverse Reaction (SUSAR)

Any AE that is both unexpected (not consistent with the applicable product information) and also meets the definition of a serious adverse reaction would be considered a suspected unexpected serious adverse reaction (SUSAR).

10.2 Laboratory Abnormalities

A clinical laboratory AE is any laboratory value that is considered clinically significant by the Investigator and has caused a medical intervention or accompanied by clinical symptoms. Laboratory abnormalities that have not required medical intervention should not be recorded as AEs and will be captured and reported in the Laboratory section of the clinical study report (CSR). If a medical intervention occurs, it should be recorded as a treatment with the abnormal laboratory finding as the AE (e.g., anemia with treatment required and blood transfusion

recorded as a procedure, hyperglycemia with treatment required and change in insulin dose recorded on concomitant medications).

The Investigator should decide, based upon the AE criteria and the clinical condition of the subject, whether a change in a laboratory parameter is clinically significant and therefore represents an AE.

If, at the end of the treatment phase with the study drug, there are pathological laboratory values which were not present at baseline, further clinical or laboratory investigations should be performed until the values return to within reference range or until a plausible explanation (i.e., concomitant disease) is found for the pathological laboratory values.

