2 OBJECTIVES AND ENDPOINTS

Objectives	Endpoints
Primary: Dose Escalation	

 To determine the MTD or the RP2D of tazemetostat when administered as an oral suspension BID in pediatric subjects with relapsed/refractory rhabdoid tumors, INI1-negative tumors, or synovial sarcoma 	
 Incidence and severity of TEAEs qualifying as protocol-defined DLTs in Cycle 1 Establishment of the protocol-defined RP2D and/or MTD
Primary: Dose Expansion	

 To evaluate the antitumor activity of tazemetostat as assessed by overall response rate (ORR) in in pediatric subjects with relapsed/refractory atypical teratoid rhabdoid tumor (ATRT) (Cohort 1), non-ATRT rhabdoid tumors (Cohort 2), INI1-negative tumors (Cohort 3), and tumor types eligible for Cohorts 1 through 3 or synovial sarcoma with SS18-SSX rearrangement (Cohort 4) using disease-appropriate standardized response criteria 	
 ORR: CR + PR for each cohort
Secondary: Dose Escalation	

 To evaluate the preliminary antitumor activity of tazemetostat as assessed by ORR, using disease-appropriate standardized response criteria 	
 ORR: CR + PR
Secondary: Dose Expansion	

 To determine the PFS and overall survival (OS) at 24 and 56 weeks and overall pediatric subjects with relapsed/refractory ATRT (Cohort 1), non-ATRT rhabdoid tumors (Cohort 2), INI1-negative tumors (Cohort 3), and tumor types eligible for Cohorts 1 through 3 or synovial sarcoma with SS18-SSX rearrangement (Cohort 4) using disease-appropriate standardized response criteria 	
 PFS at 24 and 56 weeks and overall for each cohort OS at 24 and 56 weeks and overall for each cohort
Secondary: All Subjects	

 To assess the safety and tolerability of tazemetostat administered as an oral suspension BID and tablet three times daily (TID) 	
 AEs, clinical laboratory tests, and other safety measures

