6.3 Dose-Limiting Toxicity (DLT)

A DLT will be determined in the first treatment cycle only (Day 1 to Day 28) of dose escalation and will be graded according to the CTCAE version 4.03. A DLT will be defined as a significant adverse reaction (with the exception of tumor progression) that occurred any time from the initial dose of study treatment through the end of the first cycle of treatment in dose escalation that meets any of the following criteria:

- **Non-hematologic toxicity:** any other Grade 3 or greater **non-hematologic** toxicity except:
 - alopecia
 - fatigue/asthenia
 - transient myalgia/arthralgia
 - Grade 3 vomiting or diarrhea that resolves to \leq Grade 2 within 48 hours (with or without supportive care)
 - Grade 3 nausea that resolves (with or without supportive care) to \leq Grade 2 within 7 days
 - Grade 3 anorexia requiring enteral or parenteral nutrition
- **Hematologic toxicity:** myelosuppression, defined as:
 - Grade 4 thrombocytopenia of any duration (by CTCAE, version 4.03) or Grade 3 thrombocytopenia with bleeding or lasting >7 days
 - Grade 4 neutropenia for five consecutive days (by CTCAE, version 4.03)
- Treatment delay of more than 14 days due to delayed recovery from a toxicity related to treatment with tazemetostat

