8.5.10 Clinical Laboratory Assessments

All clinical laboratory assays will be performed at local laboratories according to the laboratory's normal procedures. Chloride levels will be analyzed at both local and central laboratories. Bromide will be collected and sent only to a central laboratory for analysis. Please see Laboratory Manual for details. Reference ranges will be supplied by the laboratory and used to assess the laboratory data for clinical significance and out of range pathological changes. Abnormal laboratory values which are unexpected or not explained by the subject's clinical condition should be repeated until confirmed, explained, or resolved. Laboratory value changes starting from the initial tazemetostat exposure will be recorded in the eCRF as an AE if clinically significant.

Hematology: Hemoglobin, hematocrit, WBC, differential blood count with ANC, and platelet count assessments are performed at Screening and at regular intervals during each treatment cycle. Also, a peripheral blood smear will be collected along with normal hematology testing at screening and on day 1 of each cycle and assessed for abnormal morphology and potential bone marrow aspirate/biopsy (see below).

Coagulation Profile: Partial thromboplastin (PT), partial thromboplastin time (PTT), and international normalized ratio (INR) are performed at Screening, as clinically indicated (for example, when an anticoagulant is started or when total bilirubin increases to 1.5 X ULN), and at Post-treatment/Early Termination.

Serum Chemistry: Serum chemistries will be performed at Screening and at regular intervals during each treatment cycle.

- Chemistries (liver function) include: alkaline phosphatase, ALT, AST, and either conjugated (direct) bilirubin (where possible), or total bilirubin
- Chemistries (renal function) include: blood urea nitrogen, creatinine, electrolytes including sodium, potassium, chloride, and bicarbonate
- Chemistries (metabolism) include: albumin, calcium, magnesium, glucose, phosphorus, total protein, and triglycerides

Bromide Levels: Bromide levels will be measured pre-dose on Day 1 of Cycle 1; on Day 1 of every cycle thereafter; and at Post-Treatment/Early Termination visit.

Urinalysis: Urinalysis testing to include at minimum: glucose, blood, protein, and pH will be performed at Screening, on Cycle 1, Day 1, and on Day 1 every cycle thereafter and at Post-Treatment/Early Termination visit.

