10.3 Other Safety Assessment Abnormalities

Other safety assessments (e.g., ECGs, radiological scans, vital signs measurements), including those that worsen from baseline and events in the medical and scientific judgment of the Investigator are considered to be clinically significant, are to be recorded as an AE or SAE, in accordance with the definitions provided in Section 10.1.1 and Section 10.1.2, respectively.

Any other safety assessment that led to an intervention, including permanent discontinuation of study treatment, dose reduction, and/or dose interruption/delay is also to be recorded as an AE or SAE.

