14.1. STUDY DRUG EXPOSURE

The following summaries of study drug exposure will be presented:

- Duration of exposure (weeks) = [(last dose date of tazemetostat – first dose date of tazemetostat) + 1]/7. Except for the first and last dose dates, this calculation is not adjusted for periods where dosing is interrupted or dose is recorded as 0.
- Total number of cycles of study drug categorized as follows:
 - Cycle 1 (Days 1-28; weeks 1-4)
 - Cycle 2 (Days 29-56; weeks 5-8)
 - Cycle 3 (Days 57-84; weeks 9-12)
 - Cycle 4 (Days 85-112; weeks 13-16)
 - Cycle 5 (Days 113-140; weeks 17-20)
 - Cycle 6 (Days 141-168; weeks 21-24)
 - Cycle 7 (Days 169-196; weeks 25-28)

- Cycles 8 through 12 (Day 197-336; weeks 29-48); Note, cycles may be summarized individually if sufficient subjects are dosed at those cycles.
- Cycle 13 or more (Day 337 and beyond; week 49 and beyond); Likewise for Cycle 13 and beyond.
- Total amount of study drug taken (mg)
- For Cohorts 1 through 3: Average dose intensity (mg BID/day) = total amount of study drug taken (mg) / [2 * duration of exposure (days)]
- For Cohort 4: Average dose intensity (mg TID/day) = total amount of study drug taken (mg) / [3*duration of exposure (days)]
- Numbers of subjects requiring dose reductions, treatment interruption or treatment discontinuation in response to AEs (based on action taken for reported AEs)

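### Protocol Section 10.2 gives conflicting tests for recording a laboratory abnormality as an AE, so an untreated, asymptomatic cytopenia that meets a DLT criterion may be missing from the AE-based DLT and dose-change tables

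*Protocol*

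**What the plan says.** Protocol Section 10.2 contains three statements that do not agree.

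- Its opening sentence makes a laboratory value an AE if the investigator finds it clinically significant and it "has caused a medical intervention or accompanied by clinical symptoms".
- Its next sentence drops the symptom route: "Laboratory abnormalities that have not required medical intervention should not be recorded as AEs". Such values go to the laboratory section of the study report. The examples of intervention are a transfusion and a change of insulin dose.
- Its second paragraph leaves it to the investigator to decide "whether a change in a laboratory parameter is clinically significant and therefore represents an AE", with no condition on treatment.

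Section 8.5.10 agrees with that second paragraph: "Laboratory value changes starting from the initial tazemetostat exposure will be recorded in the eCRF as an AE if clinically significant". Section 10.1.1 includes abnormal laboratory findings in the general definition of an AE. Section 10.5 requires elevated bromide to be reported in the manner of an SAE, whatever its seriousness. Section 10.3, on assessments other than laboratory tests, makes recordable "Any other safety assessment that led to an intervention, including permanent discontinuation of study treatment, dose reduction, and/or dose interruption/delay".

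On the counting side, the hematologic DLTs in Section 6.3 include "Grade 4 thrombocytopenia of any duration", Grade 3 thrombocytopenia beyond 7 days, and Grade 4 neutropenia for five days in a row. The primary escalation endpoint in Section 2 is "Incidence and severity of TEAEs qualifying as protocol-defined DLTs in Cycle 1". SAP 17.1 likewise presents DLTs as a category of TEAE. SAP 14.1 counts subjects with dose reductions, interruptions or discontinuation "based on action taken for reported AEs".

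**The concern.** A low platelet or neutrophil count can meet Section 6.3 without symptoms and without treatment. If the site follows the restrictive sentence of 10.2, that value never reaches the AE form. An endpoint defined as a subset of TEAEs then cannot count it. If the count also held dosing, it may be missing from SAP 14.1 too.

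Sites that follow 8.5.10 will record the same event, so the DLT and cytopenia rates would depend partly on which section a site read. In a design that turns on one against two DLTs in six subjects, a single unrecorded event can matter.

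The issue outlives escalation. The final DLT, TEAE and dose-change tables are still to be produced. Section 3.4.2 also convenes the Clinical Safety Review Committee (CSRC) if DLT conditions are met in at least 33% of an expansion cohort.

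**Working it through.** The plan states no figure that depends on this rule, so the check is mainly a comparison of text.

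**Step 1. Apply each rule to two cases.** Case A is an asymptomatic, untransfused Grade 4 platelet count in Cycle 1 with dosing continued. Case B is the same count with dosing held.

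| Rule | Case A | Case B |
|---|---|---|
| 10.1.1 | Can be an AE | Can be an AE |
| 8.5.10 | AE if judged clinically significant | Same |
| 10.2, opening sentence | Not an AE | Depends on whether a hold is an intervention |
| 10.2, next sentence | Not an AE | Depends on the same point |
| 10.2, second paragraph | AE if judged clinically significant | Same |
| 10.3 | Covers other assessments | Would be an AE if it covered laboratory values |

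Case A has no consistent answer. Case B turns on a term that 10.2 does not define. Case B will also arise in practice: Table 7 interrupts treatment for Grade 3 neutropenia on the neutrophil count itself.

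**Step 2. Follow case A to the tables.** Section 6.3 makes it a DLT if it is an adverse reaction. Section 10.1.3 ties that term to suspected causality, and Section 10.7 has the investigator judge relationship for each AE or SAE. A value kept off the AE form therefore has no recorded causality and no route into a TEAE-based table. Neither document says that a laboratory value meeting a DLT criterion, or changing dosing, must be recorded as an AE.

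**Step 3. Find where the value is still visible.** Section 11 gives the CSRC laboratory values and dosing records as well as AEs. SAP 17.2 tabulates and lists Grade 3-4 values regardless of AE status, and SAP 14 lists dose interruptions and modifications. The SAP 17.2 summaries, however, take the worst value over the whole post-baseline period. They do not isolate Cycle 1, apply the durations in 6.3, or feed the DLT count.

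**Step 4. Look for evidence of loss.** Section 1.6.5 reports TEAEs leading to interruption in 90 pediatric subjects: platelet count decreased 7% (0.07 × 90 = 6.3, about 6 subjects), and thrombocytopenia and neutropenia 2% each (about 2 subjects each). Platelet terms led to dose reduction in 3 and 2 subjects. The terms may overlap. These are recorded events, so they show that the event type occurs, not how many were missed.

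**Step 5. Scale, under assumptions.** Let p be the true DLT rate and f the share of DLTs not recorded. The documents give neither. With six evaluable subjects and q = p(1 − f), the chance of 0 or 1 recorded DLT, which is the escalate decision, is (1 − q)^6 + 6q(1 − q)^5. For p = 0.33 and f = 0 this is 0.67^6 + 6 × 0.33 × 0.67^5 = 0.0905 + 0.2673 = 0.358.

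| p | f = 0 | f = 10% | f = 25% | f = 50% |
|---|---|---|---|---|
| 20% | 0.655 | 0.704 | 0.776 | 0.886 |
| 33% | 0.358 | 0.427 | 0.540 | 0.741 |
| 50% | 0.109 | 0.164 | 0.274 | 0.534 |

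For given p and f, the shift from the f = 0 column is an upper bound, because it assumes that the CSRC's review of laboratory values catches none of the unrecorded DLTs.

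**The case against.** The strongest reply is that 10.2 as a whole is not a prohibition. Its second paragraph, 8.5.10 and 10.1.1 all let the investigator record a clinically significant value, and most investigators would judge a DLT-grade cytopenia significant. This stands: the defect is a conflict between sections, and the consequence is that events may be missed, not that they will be.

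Second, a dose hold may itself be a medical intervention. The transfusion and insulin cases are only examples, and 10.3 describes discontinuation, reduction and interruption as interventions. This also stands as a fair reading, but 10.2 does not adopt it and 10.3 is confined to other assessments.

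Third, a DLT exists by virtue of 6.3, whatever is on the AE form. The DLT population refers to 6.3, and Protocol 14.5.1 speaks of DLTs without calling them TEAEs. That protects the CSRC's decisions more than the final tables, because the endpoint and SAP 17.1 are both worded in terms of TEAEs.

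Fourth, the bromide rule in 10.5 is better read as a specific rule beside a general one than as a contradiction. Asymptomatic bromide elevations were reported in 3 of 90 subjects (Section 1.4.2). That is accepted. Section 10.5 belongs in the reconciliation only so that the general sentence cannot be read as overriding it.

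**Conclusion.** The conflict is real, and it bears on the primary escalation endpoint, the SAP 17.1 DLT summary and the SAP 14.1 dose-change count. Read literally, 10.2 can leave an untreated, asymptomatic laboratory-defined DLT out of all three. It can do the same to one that held dosing, if a hold is not an intervention. The size of any loss cannot be derived from the documents. The probabilities above rest wholly on assumed values of p and f.

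Three stronger conclusions are not supported.

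- A reader might infer that cytopenias have dropped out of the AE data. Section 1.6.5 shows them recorded as TEAEs with dosing actions, so wholesale loss has not occurred. Those counts do not measure loss and cannot exclude some.
- A reader might infer that escalation went wrong. Section 1.5.2.2 reports no DLTs at 1200 mg/m², and escalation stopped there because of bromide levels and pharmacodynamic data. No dose level is identified at which one more DLT would have changed the decision, and the CSRC's remit includes laboratory values.
- A reader might infer that myelosuppression will be hidden from the report. SAP 17.2 shows Grade 3-4 values independently of AE recording. Only the AE-based tables are exposed.

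**What to change.** In the protocol, reconcile 10.2 with 6.3, 8.5.10, 10.1.1, 10.3 and 10.5. State that a laboratory abnormality is recorded as an AE, whether or not it was treated, if any of these holds:

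- it meets a Section 6.3 DLT criterion;
- it leads to dose interruption, reduction or discontinuation;
- it is an event of clinical interest under 10.5;
- the investigator judges it clinically significant.

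In the SAP, cross-check the DLTs in the DLT population against Cycle 1 laboratory and dosing data, and list any qualifying value that was not recorded as an AE. Scheduled Cycle 1 hematology is weekly (Days 1, 8, 15 and 22), so scheduled values alone cannot establish five consecutive days of Grade 4 neutropenia or more than 7 days of Grade 3 thrombocytopenia. The derivation should therefore use unscheduled values and send unresolved cases to case review.

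The cost is one protocol paragraph and one SAP derivation with its listing, from data already collected. Reported cytopenia rates may rise slightly.
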